2.4.2 Prior, concomitant and post therapies

Prior medications are defined as drugs taken and stopped prior to the first dose of study treatment. Any medication given at least once between the day of the first dose of the study treatment and the last study visit will be a concomitant medication, including those that were started pre-baseline visit and continued into the treatment period. Prior or concomitant medication will be identified based on recorded or imputed start and end dates of taking the medication.

Prior and concomitant medications and concomitant significant non-drug therapies will be summarized by treatment group (separately for ocular and non-ocular medications/therapies), presented in alphabetical order by ATC classification codes and preferred term. The tables will be presented with overall number and percentage of subjects receiving at least one drug of a particular ATC code and at least one drug in a particular preferred term. Medications will be coded according to the WHO Drug Reference List dictionary. In addition, all information will be listed including the reported name, laterality, and treatment start/end date, etc.

Moreover, concomitant medications as well as significant non-drug therapies that are prohibited as per protocol (refer to [Table 2-3](#) below) and given during the conduct of the study will be provided, separately for ocular and non-ocular medications/therapies. Summary tables on the start, stop or change dosing of the following treatments ([Table 2-4](#)) after the screening visit, unless as part of the study protocol will also be shown.

Table 2-3 Prohibited medications and therapies

Medication/therapy	Prohibition period	Action taken
Intraocular surgery or laser surgery of any kind in either eye, including cataract extraction	Any time after screening and throughout the study	Discontinue study treatment
[REDACTED]	[REDACTED]	[REDACTED]
Other investigational medicinal product or therapy	Any time after screening and throughout the study	Discontinue study treatment

Therapy for presbyopia other than optical correction (e.g., supplements, medications, training exercises, ciliary body electrostimulation, corneal implants, surgery)	Any time after screening and throughout the study	Discontinue study treatment
---	---	-----------------------------

Table 2-4 Prohibited medication changes

Medication	Prohibition period	Action taken
Antipsychotics	Any time after screening and throughout the study	Record changes in the concomitant medication eCRF and report this protocol violation; subject can stay on study drug
Antidepressants	Any time after screening and throughout the study	Record changes in the concomitant medication eCRF and report this protocol violation; subject can stay on study drug
Anticholinergics	Any time after screening and throughout the study	Record changes in the concomitant medication eCRF and report this protocol violation; subject can stay on study drug
Calcium channel blockers	Any time after screening and throughout the study	Record changes in the concomitant medication eCRF and report this protocol violation; subject can stay on study drug
Glaucoma medications	Any time after screening and throughout the study	Record changes in the concomitant medication eCRF and report this protocol violation; subject can stay on study drug
Psychostimulants	Any time after screening and throughout the study	Record changes in the concomitant medication eCRF and report this protocol violation; subject can stay on study drug
Alpha-adrenergic agonists	Any time after screening and throughout the study	Record changes in the concomitant medication eCRF and report this protocol violation; subject can stay on study drug
Any over-the counter or prescription ocular medications (except artificial tear products)	Any time after screening and throughout the study	Record changes in the concomitant medication eCRF and report this protocol violation; subject can stay on study drug

Medication	Prohibition period	Action taken
Any other medications assessed by the investigator known to affect accommodation, pupil size or near vision	Any time after screening and throughout the study	Record changes in the concomitant medication eCRF and report this protocol violation; subject can stay on study drug

2.5 Analysis of the primary objective

The primary objective of the study is to assess the efficacy of UNR844-Cl on binocular DCNVA in presbyopic subjects aged 45 to 55 years.

2.5.1 Primary endpoint

The primary estimand is defined as follows:

- Population - subjects aged 45 to 55 years in the FAS with at least one post-baseline binocular DCNVA assessment
- Variable - change in ETDRS letter score from baseline in binocular DCNVA
- Intercurrent events - data collected after any use of prohibited medications or therapies (Table 2-3), after prohibited medication changes (Table 2-4) or after discontinuation of study treatment will not be included in the estimand and will be treated as missing and imputed as described in Section 2.5.3.
- Population level summary - difference in variable means between treatment conditions at Month 3.

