#### **12.4.1 Definition of primary endpoint(s)**

The primary estimand is defined as follows:

- Population - subjects aged 45 to 55 years in the FAS with at least one post-baseline binocular DCNVA assessment

- Variable - change in ETDRS letter score from baseline in binocular DCNVA
- Intercurrent events - data collected after any use of prohibited medications or therapies (Table 6-2), after prohibited medication changes (Table 6-3) or after discontinuation of study treatment will not be included in the estimand and will be treated as missing and imputed as described in Section 12.4.3
- Population level summary - difference in variable means between treatment conditions at Month 3

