2.2 Analysis sets

The **Full Analysis Set** (FAS) comprises all subjects to whom study treatment has been assigned by randomization. According to the intent to treat principle, subjects will be analyzed according to the treatment and strata they have been assigned to during the randomization procedure. FAS will be used for all efficacy variables, unless otherwise stated.

The **Safety Set** (SAF) includes all subjects who received at least one dose of study treatment. Subjects will be analyzed according to the study treatment received, where treatment received is defined as the randomized/assigned treatment if the subject took at least one dose of that treatment or the first treatment received if the randomized/assigned treatment was never administered.

Rules of exclusion criteria of analysis sets with protocol deviations and subject classification are specified in [Appendix 5.3](#).

The number and percentage of subjects within each of the above analysis sets will be summarized.

[REDACTED]

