2.5.2 Statistical hypothesis, model, and method of analysis

The primary efficacy endpoint, change from baseline in binocular DCNVA, will be analyzed at Month 3 based on the data observed in the FAS population, according to the treatment group subjects were randomized to and the strata that were assigned at randomization. The strata information will be based on the data obtained from Interactive Response Technology (IRT) that was utilized for randomization. The comparison between the two treatment groups will be performed using a two group t-test at one-sided 5% level of significance.

Assuming general linear model for change from baseline in binocular DCNVA, the following hypotheses will be tested:

$$H_0: \delta_1 = 0 \text{ vs. } H_a: \delta_1 > 0$$

where δ_1 is the difference of change from baseline in numbers of letters read correctly between the UNR844-Cl and placebo at Month 3.

A mixed effect model repeat measurement (MMRM) model with the change from baseline in binocular DCNVA will be fitted. The model will include the change from baseline in binocular DCNVA as the dependent variable, binocular DCNVA at baseline (on its original continuous scale) as the covariate, treatment group and age group stratum at randomization, assessment visit, interaction of treatment group and assessment visit as the fixed effects and subject as a random effect. For subjects who do not have a binocular DCNVA assessment at Month 3, the predicted values of the individual subject based on the multiple imputation will be used as

dependent variable for the primary endpoint analysis and one of the supportive analysis ([Section 2.5.3](#)).

The p-value will be adjusted to one-sided, and is calculated as follows:

- $0.5 \times (\text{original two-sided p-value})$ if the least squares mean difference of UNR844 versus placebo is greater than 0
- $1 - 0.5 \times (\text{original two-sided p-value})$ if the least squares mean difference of UNR844 versus placebo is smaller than or equal to 0.

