2.5.3 Handling of missing values/ multiple values/ censoring/ discontinuations

The details of data handling for the primary efficacy endpoint are described below.

If more than one DCNVA score is recorded for each eye or both eyes at a scheduled visit, this will be handled as follows:

- Any score of “100” will be ignored;
- Of the remaining scores, the one that was entered last will be used.

For subjects who either (1) fulfilled the protocol definition of having taken prohibited medications or therapy, or made prohibited medication changes ([Section 2.4.2](#)), or (2) discontinued study treatment permanently, the data collected following either scenario (1) or (2) will be excluded and treated as missing and imputed as follows.

- For scenario (1) and (2) with reason for discontinuation being either adverse event or unsatisfactory therapeutic effect, Copy Increment from Reference (CIR) method will be used for imputation.
- For all others, the Missing at Random (MAR) imputation approach with the Five Macros (Carpenter et al. 2013) will be used for imputation.

The prohibited medications and therapies, as well as prohibited medication changes will be identified through PDs. Data after (identified through PD start date) the use of prohibited medications or therapies will be excluded. Also, data after the prohibited medication change (identified through PD start date of a new PD for the changed prohibited medication) will be excluded.

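### The primary estimand population requires a post-baseline DCNVA, so it drops randomised subjects who never return, including active-arm dropouts whom the CIR rule would otherwise impute near the placebo mean

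*SAP*

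**What the plan says.** SAP 2.2 (and Protocol 12.1) sets the FAS as the broadest possible set: it "comprises all subjects to whom study treatment has been assigned by randomization". It adds the principle "According to the intent to treat principle, subjects will be analyzed according to the treatment and strata they have been assigned to", then a general rule with an exception clause: "FAS will be used for all efficacy variables, unless otherwise stated".

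SAP 2.5.1 then takes the primary estimand population to be "subjects aged 45 to 55 years in the FAS with at least one post-baseline binocular DCNVA assessment", and Protocol 12.4.1 has the same restriction. Neither document gives a reason. SAP 2.5.2 does not repeat the condition and says only that the endpoint "will be analyzed at Month 3 based on the data observed in the FAS population".

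On missing data, SAP 2.5.3 (and Protocol 12.4.3) removes values collected after study treatment is stopped and then imputes. For "reason for discontinuation being either adverse event or unsatisfactory therapeutic effect, Copy Increment from Reference (CIR) method will be used for imputation". Other missing values are imputed under missing at random (MAR).

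SAP 2.5.4 lists two supportive analyses. The first differs from the primary only in using data collected after the intercurrent events. The second uses the observed end-of-treatment value and imputes nothing.

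**The concern.** Whether a subject has a post-baseline DCNVA is known only after randomisation and can depend on treatment. A population defined that way is no longer the one that randomisation balanced.

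The usual defence is that a subject with no post-baseline data contributes nothing under MAR. That defence does not cover everyone here. A UNR844 subject who stops for an adverse event or lack of effect, and never returns for a DCNVA, would come under CIR. With no earlier active-arm increment to carry forward, CIR gives that subject about the placebo mean change, which is no drug benefit. The restriction takes the subject out before the rule can act. If such subjects occur mainly on active drug, the estimated difference moves in the drug's favour.

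The boundary is also unclear. Suppose two subjects stop treatment for an adverse event in the first week. One attends an early-exit visit with DCNVA. The other is followed only by telephone, which Protocol 9.1.1 permits. The first subject's DCNVA falls after discontinuation, so it is set to missing. Neither has a usable value, yet the first appears to stay in the population and the second is dropped. The text does not say whether an assessment after discontinuation counts for entry, so two programmers could build different primary populations.

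**Working it through.** **Inputs**
- Effect 4.9 letters, SD 6.02, 33 completers per arm, one-sided 5%, stated power 94%, 72 enrolled (SAP 3.1.1, Protocol 12.8.1).
- 1:1 allocation within strata (SAP 1.1), so 72/2 = 36 per arm. This is an assumption, since exact balance is not guaranteed.
- Prior study: 50 subjects on UNR844 (Protocol 1.1), no discontinuations for an adverse event (Protocol 4.5).
- k = number of active subjects aged 45 to 55 with no post-baseline DCNVA who stopped for an adverse event or lack of effect. The documents do not give it; 0 to 2 is assumed.

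**Step 1: the plan's own figure.** The standard error is 6.02 × √(2/33) = 1.48 letters. Then 4.9/1.482 − 1.645 = 1.66, giving 95.2% power by the normal approximation. The noncentral t gives 94.8%. The stated 94% reproduces. For enrolment, 66/0.9 = 73.3, or 74 against the stated 72, which is close enough.

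**Step 2: shift in the estimate.** Leave k subjects out and the targeted difference stays at 4.9. Include them by CIR at the placebo mean and it becomes 4.9 × (36 − k)/36. The gap is 4.9 × k/36.

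| k | All randomised, CIR (letters) | Restricted (letters) | Gap (letters) | Gap as % of 4.9 |
|---|---|---|---|---|
| 0 | 4.90 | 4.90 | 0 | 0 |
| 1 | 4.76 | 4.90 | 0.14 | 2.8 |
| 2 | 4.63 | 4.90 | 0.27 | 5.6 |

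**Step 3: planned power.** This uses the noncentral t with 36 − k against 36 for the restricted set, and 36 against 36 for all randomised. In the latter, the active-arm variance is widened to 6.02² + q(1 − q) × 4.9², with q = k/36. A simulation with Rubin's rules (Month 3 only, 3,000 runs, 25 imputations) checks the all-randomised figures.

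| k | Restricted | All randomised | All randomised, simulated |
|---|---|---|---|
| 1 | 96.0% | 95.2% | 95.6% |
| 2 | 95.8% | 94.0% | 94.9% |

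**Step 4: is 0 to 2 reasonable?** With 0 adverse-event discontinuations in 50, the one-sided 95% upper bound is 1 − 0.05^(1/50) = 5.8%, and 0.058 × 36 = 2.1 subjects. That bound covers stopping at any time in up to three months. The affected group must also have no DCNVA at any later visit, so it should be smaller. The bound does not cover discontinuation for lack of effect, for which the documents give no prior figure.

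**Step 5: direction.** A placebo subject imputed by CIR, or any subject imputed by MAR, is expected to sit at the mean of their own arm. Excluding them does not move the expected difference. Only the active-arm CIR group does.

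**The case against.** The restriction is stated identically in both documents, and the exception clause in SAP 2.2 permits it. A reader might infer a flat contradiction with the FAS definition. The documents do not support that: this is an unexplained departure from the intent-to-treat principle, made by a route the plan leaves open.

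A reader might also infer that every early adverse-event dropout is lost. On the plain wording that is not so. Protocol 9.1.1 keeps treatment discontinuers in the study and asks them to return where possible. Protocol 8 schedules those leaving the study for a visit with the final-visit assessments, and Table 8-1 includes DCNVA there. SAP 2.1.1.3 maps such visits to a planned visit. One such assessment appears to keep the subject in, and CIR then applies. Only those who never return for a DCNVA are dropped.

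Nor is bias towards the drug shown. Protocol 4.5 reports more eye irritation (6% against 0%) and dysgeusia (14% against 0%) on active, but conjunctival hyperaemia at 8% on placebo against 0% on active, and no adverse-event discontinuations.

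Finally, it is tempting to say that the primary and secondary endpoints use different populations. SAP 2.7.2 does omit the restriction, but so does the primary model section, and SAP 5.2.2 derives the secondary response from the primary imputed data sets. Two populations are not demonstrated; the text simply leaves the secondary population unstated.

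These points limit the size and reach of the concern. They supply neither a reason for the restriction nor an analysis that restores the excluded subjects.

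**Conclusion.** The point holds in limited form. The primary population is conditioned on a post-randomisation event without justification, it can exclude active-arm subjects whom the imputation rule would otherwise place near the placebo mean, and no planned analysis checks the effect.

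The likely size is small: 0 to 0.27 letters, or 0 to 5.6% of the assumed effect, against a standard error of about 1.48 letters. Planned power with all randomised subjects is 94% or more across that range. The size rests on 36 active subjects, a 4.9-letter effect, 0 to 2 affected subjects, and every one of them being an active-arm adverse-event or lack-of-effect dropout. If none occurs, the estimate is unchanged. This is an inexpensive improvement and does not threaten the trial's main conclusion.

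**What to change.** In Protocol 12.4.1 and SAP 2.5.1, define the primary population as all randomised subjects aged 45 to 55 years with a baseline binocular DCNVA. Impute those without post-baseline data by the existing CIR and MAR rules, according to the reason for stopping. State in SAP 2.7 that the secondary endpoint uses the same imputed population. The current restricted population can stay as a supportive analysis.

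If the sponsor prefers to keep the restriction for the primary analysis, the minimum is to give a reason, say whether an assessment after discontinuation counts for entry, report exclusions by arm and reason, and add an all-randomised sensitivity analysis.

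Either change should be made before unmasking. If only the SAP is changed, its section 4, which now records no departures from the protocol, must say so. The cost is wording, a few more imputed subjects, a check that the imputation step keeps subjects with baseline data only, and an estimate that may be slightly less favourable to the drug.

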2.5.2 Statistical hypothesis, model, and method of analysis

The primary efficacy endpoint, change from baseline in binocular DCNVA, will be analyzed at Month 3 based on the data observed in the FAS population, according to the treatment group subjects were randomized to and the strata that were assigned at randomization. The strata information will be based on the data obtained from Interactive Response Technology (IRT) that was utilized for randomization. The comparison between the two treatment groups will be performed using a two group t-test at one-sided 5% level of significance.

Assuming general linear model for change from baseline in binocular DCNVA, the following hypotheses will be tested:

$$H_0: \delta_1 = 0 \text{ vs. } H_a: \delta_1 > 0$$

where δ_1 is the difference of change from baseline in numbers of letters read correctly between the UNR844-Cl and placebo at Month 3.

A mixed effect model repeat measurement (MMRM) model with the change from baseline in binocular DCNVA will be fitted. The model will include the change from baseline in binocular DCNVA as the dependent variable, binocular DCNVA at baseline (on its original continuous scale) as the covariate, treatment group and age group stratum at randomization, assessment visit, interaction of treatment group and assessment visit as the fixed effects and subject as a random effect. For subjects who do not have a binocular DCNVA assessment at Month 3, the predicted values of the individual subject based on the multiple imputation will be used as

dependent variable for the primary endpoint analysis and one of the supportive analysis ([Section 2.5.3](#)).

The p-value will be adjusted to one-sided, and is calculated as follows:

- $0.5 \times (\text{original two-sided p-value})$ if the least squares mean difference of UNR844 versus placebo is greater than 0
- $1 - 0.5 \times (\text{original two-sided p-value})$ if the least squares mean difference of UNR844 versus placebo is smaller than or equal to 0.

2.5.3 Handling of missing values/ multiple values/ censoring/ discontinuations

The details of data handling for the primary efficacy endpoint are described below.

If more than one DCNVA score is recorded for each eye or both eyes at a scheduled visit, this will be handled as follows:

- Any score of “100” will be ignored;
- Of the remaining scores, the one that was entered last will be used.

For subjects who either (1) fulfilled the protocol definition of having taken prohibited medications or therapy, or made prohibited medication changes ([Section 2.4.2](#)), or (2) discontinued study treatment permanently, the data collected following either scenario (1) or (2) will be excluded and treated as missing and imputed as follows.

- For scenario (1) and (2) with reason for discontinuation being either adverse event or unsatisfactory therapeutic effect, Copy Increment from Reference (CIR) method will be used for imputation.
- For all others, the Missing at Random (MAR) imputation approach with the Five Macros (Carpenter et al. 2013) will be used for imputation.

The prohibited medications and therapies, as well as prohibited medication changes will be identified through PDs. Data after (identified through PD start date) the use of prohibited medications or therapies will be excluded. Also, data after the prohibited medication change (identified through PD start date of a new PD for the changed prohibited medication) will be excluded.

2.5.4 Supportive analyses

There will be two supportive analyses

Supportive analysis #1:

The efficacy endpoint for Supportive analysis #1 is change from baseline in binocular DCNVA at Month 3 regardless of whether or not the intercurrent events occurred. The only difference between this analysis and the primary efficacy analysis is the inclusion of the data points after use of prohibited medications or therapy, prohibited medication changes or treatment discontinuation.

All data collected will be included in this analysis and the same imputation methods as those for the primary efficacy endpoint will be used to impute the time points that the data was truly missing.

Supportive analysis #2:

The efficacy endpoint for Supportive analysis #2 is change from baseline in binocular DCNVA at the end of treatment, i.e., the time when last study treatment is administered, which is always observed. There is no missing data imputation for the efficacy endpoint of this supportive analysis.

2.6 Analysis of the key secondary objective

There is no key secondary objective for the study.

2.7 Analysis of secondary efficacy objectives

The secondary endpoint for efficacy is the proportion of subjects aged 45 to 55 years achieving 75 or more ETDRS letters in binocular DCNVA at Month 3 after UNR844-CI or placebo treatment.

